12.5.2 Analysis Plans for Secondary Endpoints

12.5.2.1 Phase 1b Analysis of Secondary Endpoints

Safety and tolerability by NCI Common Terminology Criteria for Adverse Events (NCI CTCAE) Version 5 on treatment with PAC-1 in combination with entrectinib in subjects with metastatic uveal melanoma.

Proportion of subjects with each grade of adverse events as defined by CTCAE v.5.0 will be computed along with 95% confidence intervals and reported in a tabular and descriptive manner.

PFS at 3 month in subjects with metastatic uveal melanoma treated with PAC-1 in combination with entrectinib.

PFS will be analyzed using the Kaplan-Meier method, and median PFS will be computed with associated 95% confidence interval. Subjects who have not progressed will be right-censored at the date of the last disease evaluation. Kaplan-Meier curves will be plotted. Data will be analyzed using the PROC LIFETEST in SAS.

ORR in subjects with metastatic uveal melanoma treated with PAC-1 in combination with entrectinib.

ORR will be estimated according to RECIST 1.1, by dividing the total number of responders (complete plus partial responses) by number of subjects with measurable disease and the exact 95% confidence interval will be computed.

DoR on treatment with PAC-1 in combination with entrectinib in subjects with metastatic uveal melanoma.

DoR will be evaluated for subjects who achieve CR or PR using the Kaplan-Meier method. For such patients, DoR is defined as the number of months from the start date of CR or PR (whichever response status is observed first) and subsequently confirmed, to the first date that recurrent or progression disease (PD) is objectively documented. If a subject dies, irrespective of cause, without documentation of recurrent or PD beforehand, then the subject's date of death will be used to denote the response end date. Subjects who have not progressed will be right-censored at the date of the last disease evaluation. Median DoR will be computed with associated 95% confidence interval, and Kaplan-Meier curves will be plotted.

OS of subjects with metastatic uveal melanoma treated with PAC-1 in combination with entrectinib.

OS will be analyzed using the Kaplan-Meier method, and median OS times will be computed with associated 95% confidence intervals. Subjects who have not died will be right-censored at the date of the last follow-up, and Kaplan-Meier curves will be plotted. Data will be analyzed using the PROC LIFETEST in SAS.

12.5.2.2 Phase 2 Analysis of Secondary Endpoints

Safety and tolerability by NCI Common Terminology Criteria for Adverse Events (NCI CTCAE) Version 5 on treatment with PAC-1 in combination with entrectinib in subjects with metastatic uveal melanoma.

Proportion of subjects with each grade of adverse events as defined by CTCAE v.5.0 will be computed along with 95% confidence intervals, and reported in a tabular and descriptive manner.

ORR in subjects with metastatic uveal melanoma treated with PAC-1 in combination with entrectinib.

ORR will be estimated according to RECIST 1.1, by dividing the total number of responders (complete plus partial responses) by number of subjects with measurable disease and the exact 95% confidence interval will be computed.

DoR on treatment with PAC-1 in combination with entrectinib in patients with metastatic uveal melanoma.

DoR will be evaluated for subjects who achieve CR or PR using the Kaplan-Meier method. For such subjects, DoR is defined as the number of months from the start date of CR or PR (whichever response status is observed first) and subsequently confirmed, to the first date that recurrent or progression disease (PD) is objectively documented. If a subject dies, irrespective of cause, without documentation of recurrent or PD beforehand, then the subject's date of death will be used to denote the response end date. Subjects who have not progressed will be right-censored at the date of the last disease evaluation. Median DoR will be computed with associated 95% confidence interval, and Kaplan-Meier curves will be plotted.

OS of subjects with metastatic uveal melanoma treated with PAC-1 in combination with entrectinib.

OS will be analyzed using the Kaplan-Meier method, and median OS times will be computed with associated 95% confidence intervals. Subjects who have not died will be right-censored at the date of the last follow-up, and Kaplan-Meier curves will be plotted. Data will be analyzed using the PROC LIFETEST in SAS.

12.5.3 Analysis Plans for Correlative Objectives

Pharmacokinetic analyses of PAC-1 and entrectinib. Compare procaspase 3 expression in tumor tissue to degree of clinical response.

Tumor specimen either collected at diagnosis or obtained at enrollment will be submitted to [name], University of Illinois and will be correlated with ORR assessed by imaging (revised RECIST 1.1 criteria). Spearman correlation will be computed using PROC CORR in SAS (Cary, NC).

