1.2 Current Treatment of Uveal Melanoma

There are more than 40 clinical trials reported in uveal melanoma with average response rate of 4%. Current standard of care is dacarbazine. In a recent randomized clinical SUMMIT trial of selumetinib in combination with dacarbazine in patients with metastatic uveal melanoma the objective response rate (ORR) was 3%, with progression-free survival (PFS) of 2.8 months in selumetinib plus dacarbazine treatment group. Three- and 6-month PFS rates were 38% and 10%, respectively.⁶ Overall survival (OS) was only 10 months.

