8.1.3 Circulating Tumor Cells (CTCs)

Subject consent will be obtained for collection of peripheral blood samples prior to treatment on Cycle 1 Day 1, Cycle 2 Day 1 and at progression (safety visit). This specimen will be analyzed for total CTCs. Spearman correlation will be computed using PROC CORR in SAS (Cary, NC). CTC number or change from Cycle Day 1 to Cycle 2 Day 1 will be correlated with ORR assessed by imaging (revised RECIST 1.1 criteria). Spearman correlation will be computed using PROC CORR in SAS (Cary, NC).

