8.2.2 Immunohistochemistry (IHC)

IHC for markers such as but not limited to procaspase 3. Determine correlation between procaspase 3 expression in tumor tissue and clinical **response**. Procaspase 3 expression will be correlated with ORR assessed by imaging (revised RECIST 1.1 criteria). Spearman correlation will be computed using PROC CORR in SAS (Cary, NC).

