12.3 Sample Size and Accrual

Previous studies in the target population identified PFS at 3 months of 38%.⁶ We hypothesize PFS at 3 months of 65%. Controlling for a probability of Type I error at 0.05 (one-sided), our sample size in Phase 2 is estimated to be 32 to ensure 90% statistical power in successfully detecting an alternative PFS rate at 3 months of 0.65, compared to a null rate of 0.38. With 3 additional patients to account for a 10% drop off rate, sample size for phase 2 study will be 35. Sample size analyses were conducted using the PASS software (NCSS, Kaysville, Utah, USA). With phase 1b study component, the study will need to have 3 subjects from Dose Level 1 of Phase 1b + 6 subjects from Dose Level 2 of Phase 1b (and carried over to Phase 2 study). The total number of subjects for the study is 38.

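### Procaspase-3 and CTC values are to be Spearman-correlated with a yes/no response outcome; percent change in target lesions, derivable from recorded measurements, would carry far more information

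*Combined protocol and SAP*

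**What the plan says.** Three places name the outcome for the biomarker analyses. Section 8.2.2: "Procaspase 3 expression will be correlated with ORR assessed by imaging". Section 12.5.3 repeats this for the tumour specimen, which "will be correlated with ORR assessed by imaging (revised RECIST 1.1 criteria". Section 8.1.3: "CTC number or change from Cycle Day 1 to Cycle 2 Day 1 will be correlated with ORR assessed by imaging". The method each time is Spearman correlation in SAS, with no alpha level or sidedness given. Section 12.5.3 has no plan for CTCs; that plan stands only in section 8.1.3.

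Section 9.9.2 defines objective response rate as the proportion of subjects with confirmed CR or PR. The procaspase-3 objective (sections 2.3, 2.6 and 12.5.3) concerns the degree of clinical response; the CTC objective says only clinical response.

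The only response rates in the document are historical, in section 1.2: "There are more than 40 clinical trials reported in uveal melanoma with average response rate of 4" per cent, and 3% in the cited randomized trial of selumetinib plus dacarbazine. No ORR is assumed for PAC-1 with entrectinib.

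Sections 9.2, 9.4 and 9.6 have lesions measured in millimetres, a baseline sum of diameters calculated, and PR and PD assigned from the percent change in that sum. Section 8 makes the correlative analyses dependent on funding.

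**The concern.** ORR is a property of a group. To correlate it with a marker, each patient has to be coded responder or non-responder. When few patients respond, nearly all share one tied rank and the coefficient rests on one or two people. A patient whose lesions shrink by 25% and one whose lesions grow by 60% then count as the same. For procaspase-3 this also fails to measure the graded response that the objective names.

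Procaspase-3 is the biological rationale for PAC-1 (section 1.4), and patients must have archival tissue or undergo a biopsy to enter (section 3.1). A null result from an analysis with little power could be misread as no relationship. Choosing a better outcome after the data are seen would be post hoc.

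**Working it through.** **Inputs.** Section 12.3 gives the Phase 2 base size: "Controlling for a probability of Type I error at 0.05 (one-sided), our sample size in Phase 2 is estimated to be 32". The power there is 90%, for a 3-month PFS of 0.65 against 0.38 under the null. On drop-off it says: "With 3 additional patients to account for a 10% drop off rate, sample size for phase 2 study will be 35". On the overall count it says: "The total number of subjects for the study is 38". Section 1.2: response rates of 3% and 4%. Assumed, because the plan is silent: two-sided 5% for the correlations, complete pairs in all 35 patients, and ORR of 10% and 20% as a sensitivity range.

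**The plan's own figure.** The plan states no sample size or power for the correlative analyses, so only the Phase 2 number can be reproduced.
- Normal approximation: [(1.645·√(0.38·0.62) + 1.282·√(0.65·0.35))/0.27]² = 27.3, so 28.
- With continuity correction: 30.9, so 31.
- Exact binomial at n = 32, success at 18 or more: alpha 0.0275, power 88.8%.

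The stated 32 is reproduced within tolerance. Then 32 + 3 = 35 for Phase 2, and 3 + 35 = 38 in total.

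**Responders expected, n = 35.** Expected number = 35·p; P(0) = (1−p)³⁵; P(≤1) = P(0) + 35·p·(1−p)³⁴.

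| ORR | Expected | P(0) | P(≤1) |
|---|---|---|---|
| 3% | 1.05 | 34% | 72% |
| 4% | 1.4 | 24% | 59% |
| 10% | 3.5 | 2.5% | 12% |
| 20% | 7.0 | <0.1% | 0.4% |

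**Best attainable result.** With no responder the outcome is constant and rho is undefined. With one responder who holds the most extreme marker value, and no ties in the marker, rho = √(3/(n+1)) = √(3/36) = 0.289. Then t = 0.289·√(33/(1−0.0833)) = 1.73 on 33 df, two-sided p = 0.093; the exact permutation value is 2/35 = 0.057. Two-sided 5% is therefore unattainable with one responder, and the same holds at n = 32 and n = 38. With two responders the smallest p is 0.017 (t approximation).

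**Overall power, n = 35, two-sided 5%.** Simulation with 20,000 runs per setting: marker and tumour change bivariate normal, responders being the patients with the greatest shrinkage, undefined rho counted as no detection. The results are good to a point or two.

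| Outcome | True rho 0.4 | True rho 0.5 |
|---|---|---|
| Yes/no, ORR 3% | 6.5% | 10% |
| Yes/no, ORR 4% | 9.6% | 15% |
| Yes/no, ORR 10% | 23-24% | 35% |
| Yes/no, ORR 20% | 34-36% | 53% |
| PR/SD/PD (ORR 3-4%, 50% PD assumed) | 49-50% | 70-71% |
| Continuous percent change | 62-63% | 84% |

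**Detectable rho with the continuous outcome, 80% power.** Fisher z: tanh(2.80/√(n−3)). At n = 35 this is tanh(2.80/√32) = 0.46, or 0.47 with the Spearman variance factor of 1.06. At n = 32 it is 0.48 to 0.49.

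**The case against.** The strongest reply is that 3% and 4% come from other treatments. The plan hypothesizes an improvement (3-month PFS of 65% against 38%) and commits to no ORR. A reader might infer that the trial expects about one responder and that the biomarker analyses therefore cannot detect anything. The documents do not support that. The responder count is conditional on the historical rates. Even at 4% there is a 41% chance of two or more responders, when significance is attainable. Since no sidedness is stated, a one-sided test could just reach 5% with a single top-ranked responder (t p = 0.046; exact 1/35 = 0.029). What remains is a large loss of power, which persists at an ORR of 10% or 20%.

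A second reply is that ORR may be shorthand for the ordered RECIST categories, which would suit a rank method and an objective about degree. That reading would recover much of the power. But section 9.9.2 defines ORR as confirmed CR or PR, and nothing in the three analysis sections says otherwise; if the ordered category is meant, the plan has to name it. The argument from degree applies to procaspase-3 only, since the CTC objective does not use that word.

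Third, these analyses are exploratory and may not be funded. That is true, and it limits the weight of the point without removing it.

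**Conclusion.** The concern holds as one of inefficient and, for procaspase-3, mismatched outcome choice. At the historical 3% to 4% rates, the planned correlation would be undefined with probability 24% to 34%. It would be unable to reach two-sided 5% with probability 59% to 72%, a figure that includes the undefined cases. Its power at rho 0.4 would be about one tenth to one sixth of what a continuous outcome gives. At an ORR of 10% to 20% it would be somewhat over a third to somewhat over a half.

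The size rests on three assumptions that the plan does not state: the ORR, two-sided 5%, and complete marker and scan data in 35 patients. With fewer pairs, power falls for every outcome. The comparison also assumes that the marker relates to tumour change across its whole range. The document does not name best percent change as a variable; it can be derived from what is recorded. No primary or secondary conclusion is affected.

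**What to change.** In sections 8.1.3, 8.2.2 and 12.5.3, replace ORR as the Spearman outcome by best percent change from baseline in the sum of target-lesion diameters, and add the CTC plan to section 12.5.3. Specify that:
- patients who die or progress before a post-baseline scan, or whose best overall response is PD through new or non-target lesions, receive the worst ranks, because the target-lesion sum does not capture such progression;
- patients without a post-baseline scan for other reasons are reported as missing, with their number;
- ordered best overall response (CR/PR/SD/PD) is a companion outcome, and responder status is tabulated descriptively;
- any Cox model relating CTC change to PFS starts its clock at a Cycle 2 Day 1 landmark, when the change becomes known, to avoid guarantee-time bias.

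State the alpha level and sidedness, or say that the analyses are descriptive.

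Cost: no new visit, scan or sample. The text sits in a combined protocol, so this is a small wording amendment that goes to the IRB (section 15.1), plus slightly more analysis. Label: cheap improvement.

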12.5.4 Other Planned Analyses

Descriptive statistics will be provided to summarize demographics and baseline characteristics parameters. Categorical data will be summarized as frequency and its corresponding percentage. For continuous data, frequency (n), mean, standard deviation, median (as appropriate), minimum, and maximum will be provided for each of the parameters.

12.6 Interim Analysis/Criteria for Stopping Study

No interim analyses are planned for this study. However, the Data Safety Monitoring Board will be reviewing study safety and treatment activity periodically and provide recommendations regarding need for stopping study. See Section 13 for additional information.

13 TRIAL MANAGEMENT**13.1 Data and Safety Monitoring Plan (DSMP)**

HCRN oversight activities include:

- Review and processing of all adverse events requiring expedited reporting as defined in the protocol
- Provide trial accrual progress, safety information and data summary reports to the sponsor-investigator
- Submit data summary reports to the DSMB for review according to DSMB Charter

This study will have a Data and Safety Monitoring Board (DSMB). The DSMB is chaired by an independent medical oncologist external to this trial. The DSMB will provide a recommendation to the sponsor-investigator after all information is reviewed. This information will also be provided to HCRN who will distribute to the site investigator/participating sites for submission to their respective IRB according to the local IRB's policies and procedures.

The DSMB review will include but is not limited to:

- Adverse event summary report
- Audit results if applicable
- Data related to stopping/decision rules described in study design
- Study accrual patterning
- Protocol deviations

The DSMB will meet twice annually during the active study drug administration phase. Additional DSMB meetings may be convened upon request of the Sponsor-Investigator, DSMB, or other applicable oversight body.

13.2 Data Quality Oversight Activities

Remote validation of the EDC system data will be completed on a continual basis throughout the life cycle of the study. Automated edit check listings will be used to generate queries in the EDC system and transmitted to the site to address in a timely fashion. Corrections will be made by the study site personnel.

Participating sites may also be subject to quality assurance audits by Genentech and Vanquish Oncology, Inc. or their designees as well as inspection by appropriate regulatory agencies.

13.2.1 Onsite Monitoring

Monitoring visits to the trial sites may be made periodically during the trial to ensure key aspects of the protocol are followed. For cause visits may occur as necessary. Selected source documents will be reviewed for verification of agreement with data entered into the EDC system. It is important for the site investigator and their relevant personnel to be available for a sufficient amount of time during the monitoring visits or audit, if applicable. The site investigator and institution guarantee access to source documents by HCRN or its designee.

The trial site may also be subject to quality assurance audit by Genentech/Roche and Vanquish Oncology, Inc. or their designees as well as inspection by appropriate regulatory agencies.

13.3 Compliance with Trial Registration and Results Posting Requirements

Under the terms of the Food and Drug Administration Modernization Act (FDAMA) and the Food and Drug Administration Amendments Act (FDAAA), the sponsor-investigator of the trial is solely responsible for determining whether the trial and its results are subject to the requirements for submission to the Clinical Trials Data Bank, <http://www.clinicaltrials.gov>. All results of primary and secondary objectives must be posted to CT.gov within a year of completion. The sponsor-investigator has delegated responsibility to HCRN for registering the trial and posting the results on clinicaltrials.gov. Information posted will allow subjects to identify potentially appropriate trials for their disease conditions and pursue participation by calling a central contact number for further information on appropriate trial locations and study site contact information.

14 DATA HANDLING AND RECORD KEEPING

14.1 Data Management

HCRN will serve as the Clinical Research Organization for this trial. Data will be collected through a web based clinical research platform, a system compliant with Good Clinical Practices and Federal Rules and Regulations. HCRN personnel will coordinate and manage data for quality control assurance and integrity. Select data will be collected and entered into the EDC system by study site personnel from participating institutions.

14.2 Case Report Forms and Submissions

Generally, clinical data will be electronically captured in the EDC system and correlative results will be captured in the EDC system or other secure database(s). If procedures on the study calendar are performed for standard of care, at a minimum, that data will be captured in the source document. Select standard of care data will also be captured in the EDC system, according to study-specific objectives.

The completed dataset is the sole property of the sponsor-investigator's institution and should not be exported to third parties, except for authorized representatives of appropriate Health/Regulatory Authorities, without permission from the sponsor-investigator and HCRN.

14.3 Record Retention

To enable evaluations and/or audits from Health Authorities/HCRN, the site investigator agrees to keep records, including the identity of all subjects (sufficient information to link records; e.g., hospital records), all original signed informed consent forms, copies of all source documents, and detailed records of drug disposition. All source documents are to remain in the subject's file and retained by the site investigator in compliance with the site contract with HCRN. No records will be destroyed until HCRN confirms destruction is permitted.

14.4 Confidentiality

There is a slight risk of loss of confidentiality of subject information. All records identifying the subjects will be kept confidential and, to the extent permitted by the applicable laws and/or regulations, will not be made publicly available. Information collected will be maintained on secure and password protected electronic systems. Paper files that contain personal information will be kept in locked and secure locations only accessible to the study site personnel.

Subjects will be informed in writing that some organizations including the sponsor-investigator and his/her research associates, HCRN, Genentech and Vanquish Oncology, Inc., the IRB, or government agencies, like the FDA, may inspect their medical records to verify the information collected, and that all personal information made available for inspection will be handled in strictest confidence and in accordance with local data protection laws.

If the results of the study are published, the subject's identity will remain confidential.

15 ETHICS

15.1 Institutional Review Board (IRB) Approval

The final study protocol and the final version of the informed consent form must be approved in writing by an IRB. The site investigator must submit written approval by the IRB to HCRN before he or she can enroll subjects into the study.

The site investigator is responsible for informing the IRB of any amendment to the protocol in accordance with local requirements. In addition, the IRB must approve all advertising used to recruit subjects for the study. The protocol must be re-approved by the IRB, as local regulations require.

Progress reports and notifications of serious and unexpected adverse events will be provided to the IRB according to local regulations and guidelines.

15.2 Ethical Conduct of the Study

The study will be performed in accordance with ethical principles originating from the Declaration of Helsinki. Conduct of the study will be in compliance with ICH Good Clinical Practice, and with all applicable federal (including 21 CFR parts 56 & 50), state, or local laws.

